## 14. ETHICAL AND REGULATORY CONSIDERATIONS

### 14.1. Good Clinical Practice Statement

It is the responsibility of both the sponsor and the investigator(s) to ensure that this clinical study will be conducted in accordance with the ethical principles that have their origin in the Declaration of Helsinki, and that are consistent with the ICH guidelines for GCP and applicable regulatory requirements.

#### Informed Consent

The principles of informed consent are described in ICH guidelines for GCP.

The ICF used by the investigator must be reviewed and approved by the sponsor prior to submission to the appropriate IRB/EC. A copy of the IRB/EC -approved ICF and documentation of approval must be provided to the sponsor before study drug will be shipped to the study site.

It is the responsibility of the investigator or designee (if acceptable by local regulations) to obtain written informed consent from each subject prior to his/her participation in the study and after the aims, methods, objectives, and potential hazards of the study have been explained to the subject in language that he/she can understand. The ICF should be signed and dated by the subject and by the investigator or authorized designee who reviewed the ICF with the subject.

- Subjects who can write but cannot read will have the ICF read to them before signing and dating the ICF.
- Subjects who can understand but who can neither write nor read will have the ICF read to them in presence of an impartial witness, who will sign and date the ICF to confirm that informed consent was given.

The original ICF must be retained by the investigator as part of the subject's study record, and a copy of the signed ICF must be given to the subject.

If new safety information results in significant changes in the risk/benefit assessment, the ICF must be reviewed and updated appropriately. All study subjects must be informed of the new information and provide their written consent if they wish to continue in the study. The original signed revised ICF must be maintained in the subject's study record and a copy must be given to the subject.

#### **14.2. Subjects Confidentiality and Data Protection**

The investigator must take all appropriate measures to ensure that the anonymity of each study subject will be maintained. Subjects should be identified by a subject identification number only, on CRFs or other documents submitted to the sponsor. Documents that will not be submitted to the sponsor (eg, signed ICF) must be kept in strict confidence.

The subject's and investigator's personal data, which may be included in the sponsor database, will be treated in compliance with all applicable laws and regulations. The sponsor shall take all appropriate measures to safeguard and prevent access to this data by any unauthorized third party.

#### **14.3. Institutional Review Board/Ethics Committee**

An appropriately constituted IRB/EC, as described in ICH guidelines for GCP, must review and approve:

- The protocol, ICF, and any other materials to be provided to the subjects (eg, advertising) before any subject may be enrolled in the study
- Any amendment or modification to the study protocol or ICF before implementation, unless the change is necessary to eliminate an immediate hazard to the subject, in which case the IRB/EC should be informed as soon as possible
- Ongoing studies on an annual basis or at intervals appropriate to the degree of risk

In addition, the IRB/EC should be informed of any event likely to affect the safety of subjects or the continued conduct of the clinical study.

A copy of the IRB/EC approval letter with a current list of the IRB/EC members and their functions must be received by the sponsor prior to shipment of drug supplies to the investigator. The approval letter should include the study number and title, the documents reviewed, and the date of the review.

Records of the IRB/EC review and approval of all study documents (including approval of ongoing studies) must be kept on file by the investigator.

### **15. PROTOCOL AMENDMENTS**

The sponsor may not implement a change in the design of the protocol or ICF without an IRB/EC-approved amendment

### **16. PREMATURE TERMINATION OF THE STUDY OR CLOSE-OUT OF A SITE**

#### **16.1. Premature Termination of the Study**

The sponsor has the right to terminate the study prematurely. Reasons may include efficacy, safety, or futility, among others. Should the sponsor decide to terminate the study, the investigator(s) will be notified in writing.

## 16.2. Close-out of a Site

The sponsor and the investigator have the right to close-out a site prematurely.

### Investigator's Decision

The investigator must notify the sponsor of a desire to close-out a site in writing, providing at least 30 days' notice. The final decision should be made through mutual agreement with the sponsor. Both parties will arrange the close-out procedures after review and consultation.

### Sponsor's Decision

The sponsor will notify the investigator(s) of a decision to close-out a study site in writing. Reasons may include the following, among others:

- The investigator has received all items and information necessary to perform the study, but has not enrolled any subject within a reasonable period of time
- The investigator has violated any fundamental obligation in the study agreement, including but not limited to, breach of this protocol (and any applicable amendments), breach of the applicable laws and regulations, or breach of any applicable ICH guidelines
- The total number of subjects required for the study are enrolled earlier than expected

In all cases, the appropriate IRB/EC and Health Authorities must be informed according to applicable regulatory requirements, and adequate consideration must be given to the protection of the subjects' interests.

## 17. STUDY DOCUMENTATION

### 17.1. Certification of Accuracy of Data

A declaration assuring the accuracy and content of the data recorded on the eCRF must be signed electronically by the investigator. This signed declaration accompanies each set of subject final eCRFs that will be provided to the sponsor.

### 17.2. Retention of Records

The investigator must retain all essential study documents, including ICFs, source documents, investigator copies of CRFs, and drug accountability records for at least 15 years following the completion or discontinuation of the study, or longer, if a longer period is required by relevant regulatory authorities. The investigator must obtain written approval from the sponsor before discarding or destroying any essential study documents during the retention period following study completion or discontinuation. Records must be destroyed in a manner that ensures confidentiality.

If the investigator's personal situation is such that archiving can no longer be ensured, the investigator must inform the sponsor (written notification) and the relevant records will be transferred to a mutually agreed-upon destination.

## 18. DATA QUALITY ASSURANCE

In accordance with ICH E6, the sponsor is responsible for quality assurance to ensure that the study is conducted and the data generated, recorded, and reported in compliance with the protocol, GCP, and any applicable regulatory requirement(s). The planned quality assurance and quality control procedures for the study are summarized.

### Data Management

The sponsor is responsible for the data management of this study including quality checking of the data (Section 11.1).

### Study Monitoring

The investigator must allow study-related monitoring, IRB/EC review, audits, and inspections from relevant health regulatory authorities, and provide direct access to source data documents (Section 12.1, Section 12.2, Section 13)

The study monitors will perform ongoing source data review to verify that data recorded in the CRF by authorized site personnel are accurate, complete, and verifiable from source documents, that the safety and rights of subjects are being protected, and that the study is being conducted in accordance with the current approved protocol version and any other study agreements, ICH GCP, and all applicable regulatory requirements (Section 12.1).

All subject/patient data collected during the study will be recorded on paper or electronic CRF unless the data are transmitted to the sponsor or designee electronically (eg, laboratory data). The investigator is responsible for affirming that data entries in the CRF are accurate and correct by electronically signing a declaration that accompanies each set of subject final CRF (Section 12.3 and Section 17.1).

### Study Documentation

The investigator must maintain accurate documentation (source data) that supports the information entered in the CRF (Section 12.2).

The investigator will retain all records and documents, including signed ICFs, pertaining to the conduct of this study for at least 15 years after study completion, unless local regulations or institutional policies require a longer retention period. No records may be destroyed during the retention period without the written approval of the sponsor. No records may be transferred to another location or party without written notification to the sponsor (Section 17.2).

## 19. CONFIDENTIALITY

Confidentiality of information is provided as a separate agreement.

## 20. FINANCING AND INSURANCE

Financing and insurance information is provided as a separate agreement.

## 21. PUBLICATION POLICY

The publication policy is provided as a separate agreement.

Allergic reaction	Transient flushing or rash, drug fever <38 degrees C (<100.4 degrees F); intervention not indicated	Intervention or infusion interruption indicated; responds promptly to symptomatic treatment (eg, antihistamines, NSAIDS, narcotics); prophylactic medications indicated for ≤24 hours	Prolonged (eg, not rapidly responsive to symptomatic medication and/or brief interruption of infusion); recurrence of symptoms following initial improvement; hospitalization indicated for clinical sequelae (eg, renal impairment, pulmonary infiltrates)	Life-threatening consequences; urgent intervention indicated	Death
Definition: A disorder characterized by an adverse local or general response from exposure to an allergen					
Anaphylaxis	–	–	Symptomatic bronchospasm, with or without urticaria; parenteral intervention indicated; allergy-related edema/angioedema; hypotension	Life-threatening consequences; urgent intervention indicated	Death
Definition: A disorder characterized by an acute inflammatory reaction resulting from the release of histamine and histamine-like substances from mast cells, causing a hypersensitivity immune response. Clinically, it presents with breathing difficulty, dizziness, hypotension, cyanosis and loss of consciousness and may lead to death.					

## LIST OF ABBREVIATIONS AND DEFINITION OF TERMS

AD	Atopic dermatitis
ADA	Anti-Drug Antibodies
AE	Adverse event
AESI	Adverse event of special interest
ALT (SGOT)	Alanine aminotransferase
ANCOVA	Analysis of covariance
AST (SGPT)	Aspartate aminotransferase
AUC	Area under curve
BAU	Bioequivalent allergy unit
BUN	Blood urea nitrogen
CRF	Case report form
ECG	Electrocardiogram
EOS	End of study
EOT	End of treatment
ET	Early termination
FAS	Full analysis set
HIV	Human Immunodeficiency Virus
HLT	High Level Term
ICF	Informed consent form
ICH	International conference on harmonization
IL	Interleukin
IgE	Immunoglobulin E
IgG4	Immunoglobulin G4

LDH	Lactate dehydrogenase
LOCF	Last observation carried forward
MedDRA	Medical Dictionary for Regulatory Activities
MI	Multiple imputation
NAb	Neutralizing Antibody
NAC	Nasal allergen challenge
PCSV	Potentially clinically significant value
PD	Pharmacodynamics
PK	Pharmacokinetic
PKAS	Pharmacokinetic analysis set
PNIF	Peak nasal inspiratory flow
PT	Preferred term
Q2W	Once every 2 weeks
RBC	Red blood cell
Regeneron	Regeneron Pharmaceuticals, Inc.
sIgE	Specific immunoglobulin E
sIgG4	Specific immunoglobulin G4
SAE	Serious adverse event
SAF	Safety analysis set
SAP	Statistical analysis plan
SAS	Statistical analysis software
SC	Subcutaneous
SCIT	Subcutaneous immunotherapy
SD	Standard deviation

SE	Standard error
SOC	System organ class
SPT	Skin prick test
TARC	Thymus and activation-regulated chemokine
TEAE	Treatment emergent adverse event
Th2	Type-2 T helper cells
TNSS	Total nasal symptom score
TOSS	Total ocular symptom score
WHODD	World health organization drug dictionary

## 1. OVERVIEW

The purpose of the statistical analysis plan (SAP) is to ensure the credibility of the study results by pre-specifying the statistical approaches for the analysis of study data prior to database lock. The SAP is intended to be a comprehensive and detailed description of the strategy and statistical methods to be used in the analysis of data for R668-ALG-16115 study.

### 1.1. Background/Rationale

Subcutaneous immunotherapy (SCIT) is a disease modifying treatment option for patients with allergic rhinitis triggered by aeroallergens (such as pollen, animal dander, or dust). SCIT is recommended when pharmacological therapies are not sufficient to control symptoms. During SCIT, increasing doses of the inciting allergen are administered, followed by a maintenance dose for several years, with the goal of inducing immunological changes leading to symptom amelioration while on therapy, as well as sustained desensitization off SCIT (immune tolerance). The pathobiology of allergic disease is complex, involving many cell types and genetic susceptibility. Data suggest that SCIT results in memory T and B cell responses, allergen-specific immunoglobulin shifts from immunoglobulin E (IgE) to immunoglobulin G (IgG), including IgG4, decreased type 2 cytokines in tissues, decreased tissue migration of eosinophils and decreased mediator release from tissue mast cells, basophils and eosinophils.

Dupilumab is a human monoclonal IgG4 antibody that inhibits interleukin-4 (IL-4) and interleukin-13 (IL-13) signaling by specifically binding to the IL-4R $\alpha$  subunit shared by the IL-4 and IL-13 receptor complexes. Blocking IL-4R $\alpha$  with dupilumab inhibits IL-4 and IL-13 cytokine-induced responses, including the release of proinflammatory cytokines, chemokines and IgE. IL-4 and IL-13 play key roles in the pathophysiology of allergic diseases, as demonstrated by dupilumab's efficacy shown in clinical studies in atopic diseases such as atopic dermatitis (AD), asthma, nasal polyposis (NP) and eosinophilic esophagitis. This is the basis for the rationale to evaluate whether dupilumab may enhance allergy immunotherapy. In a post-hoc analysis of a dupilumab dose-ranging study in moderate-to-severe asthma patients with comorbid allergic rhinitis, patients had a significant reduction in reported rhinitis symptoms with dupilumab compared to placebo. Because of these data and the role of IL-4 and IL-13 in immunoglobulin class switching, we anticipate that dupilumab as an adjunct to SCIT, will enhance the change of allergen specific IgG/IgE ratio, in SCIT + dupilumab treated subjects as compared to subjects treated with SCIT alone.

There is an unmet need for a more efficacious treatment of allergic disease. SCIT can provide long-lasting protection from allergic disease, but it also carries a risk of adverse reactions, has variable efficacy between patients, and can take at least 3 years to induce immune tolerance. Induction of type 2 pathway cytokines upon SCIT initiation can transiently exacerbate allergic symptoms, resulting in SCIT dose limitations during up-titration in some patients. Blockade of these cytokines by dupilumab may improve tolerability of the desensitization process, in addition to improving overall safety and efficacy by further suppression of IgE production.

This trial is a 4-arm, placebo-controlled, double-blind, randomized, parallel-group, proof-of-concept (phase 2a) study over a 16-week treatment period followed by an 8-week safety follow-up period in approximately 100 adult subjects with a history of Timothy Grass-induced allergic

rhinitis. Four treatment groups after 600mg loading dose are required to provide informative controls and minimize bias on clinical endpoints:

- dupilumab + SCIT
- SCIT
- dupilumab
- placebo.

In addition, this study will allow the evaluation of dupilumab monotherapy on clinical rhinitis symptoms and related biomarkers.

## **1.2. Study Objectives**

### **1.2.1. Primary Objectives**

The primary objective of the study is to assess whether 16 weeks of treatment with dupilumab as an adjunct to Timothy Grass SCIT improves upon the efficacy of Timothy Grass SCIT to reduce provoked allergic rhinitis symptoms, as measured by TNSS after NAC with Timothy Grass extract at week 17.

### **1.2.2. Secondary Objectives**

The secondary objectives of the study are

- To assess whether 16 weeks of treatment with dupilumab as compared to placebo reduces provoked allergic rhinitis symptoms, as measured by TNSS after NAC with Timothy Grass extract
- To assess whether 16 weeks of treatment with dupilumab as compared to dupilumab + SCIT reduces provoked allergic rhinitis symptoms, as measured by TNSS after nasal allergen challenge (NAC) with Timothy Grass extract
- To assess changes in serum Timothy-grass-specific IgG4, serum Timothy Grass-specific IgE, and ratio of serum Timothy Grass-specific IgG4 to IgE over 16 weeks of treatment with dupilumab + SCIT as compared to SCIT monotherapy
- To evaluate the safety and tolerability of 16 weeks of treatment with dupilumab as an adjunct to Timothy Grass SCIT

### **1.2.3. Other Objectives**

- To assess whether 16 weeks of treatment with dupilumab as an adjunct to Timothy Grass SCIT improves upon the efficacy of Timothy Grass SCIT to reduce provoked allergic conjunctivitis symptoms, as measured by TOSS after NAC with Timothy Grass extract.
- To assess whether 16 weeks of treatment with dupilumab as compared to placebo reduces provoked allergic conjunctivitis symptoms, as measured by TOSS after NAC with Timothy Grass extract.

- To assess the changes in both early-phase (0–1 hr) and late-phase (1-6 hr) skin responses following Skin Prick Test with Serial Allergen Titration and intradermal administration of Timothy Grass, respectively, over 16 weeks of treatment with dupilumab, SCIT, dupilumab + SCIT, and placebo
- To assess changes in peak nasal inspiratory flow (PNIF) after NAC over 16 weeks of treatment with dupilumab, SCIT, dupilumab + SCIT, and placebo
- To assess total sneeze count after NAC over 16 weeks of treatment with dupilumab, SCIT, dupilumab + SCIT, and placebo
- To assess changes in serum TARC over 16 weeks of treatment with dupilumab, SCIT, dupilumab + SCIT, and placebo
- To assess changes in serum total IgE over 16 weeks of treatment with dupilumab, SCIT, dupilumab + SCIT, and placebo
- To assess changes in serum Timothy-grass-specific IgG and ratio of serum Timothy Grass-specific IgG to IgE over 16 weeks of treatment with dupilumab + SCIT as compared to SCIT
- To assess whether dupilumab as an adjunct to SCIT improves SCIT tolerability, defined as an increase in the proportion of subjects who achieve SCIT maintenance dose (4000 BAU), comparing 16 weeks of treatment with dupilumab + SCIT and 16 weeks of treatment with SCIT
- To assess whether dupilumab as an adjunct to SCIT improves SCIT tolerability, defined as an increase in the maximal tolerated SCIT dose, comparing 16 weeks of treatment with dupilumab + SCIT and 16 weeks of treatment with SCIT
- To evaluate the effects of treatment (dupilumab + SCIT vs SCIT) on local skin wheal size, measured approximately 15 minutes after each SCIT injection.

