There is an unmet need for a more efficacious treatment of allergic disease. SCIT can provide long-lasting protection from allergic disease, but it also carries a risk of adverse reactions, has variable efficacy between patients, and can take at least 3 years to induce immune tolerance (Durham, 1999) (Durham, 2012) (Leung, 2010) (Durham, 2016). At the start of SCIT, patients receive injections of increasing doses of the allergen at weekly intervals over several weeks to months, under tightly monitored medical supervision. The gradual dose escalation enables tolerability to therapy and mitigates risk of severe hypersensitivity reactions related to allergen administration. Side effects occur in 40-50 % of patients ranging from mild reactions (eg, swelling, injection site reaction, de novo allergic response, and urticaria) to life-threatening reactions (eg, asthma exacerbation and anaphylaxis) (Frew, 2006a). Asthma is a major risk factor for life-threatening systemic reactions to SCIT and therefore moderate-severe asthma is a contraindication to SCIT. Therefore with proper patient selection, risk of severe reactions can be mitigated (Frew, 2010) (Frew, 2006a). Induction of Type 2 pathway cytokines upon SCIT initiation can transiently exacerbate allergic symptoms, resulting in SCIT dose limitations during up-titration in some patients. Blockade of these cytokines by dupilumab may improve tolerability of the desensitization process, in addition to improving overall safety and efficacy by further suppression of IgE production.

Therefore, dupilumab may: 1) limit symptoms of the desensitization process so that maximal SCIT up-titration may be achieved 2) improve the efficacy of the sensitization process via its suppressive effect on IgE production, and 3) reduce allergic symptoms directly by other mechanisms including the inhibition of allergen specific Type 2 t-cells (Th2) cell number and function with downstream effects on mast cells, eosinophils, and basophils.

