- Change from baseline (last pretreatment measurement) to week 17 in log-transformed value of serum Timothy Grass sIgG to Timothy Grass sIgE ratio for dupilumab + SCIT as compared to SCIT
- Proportion of subjects who achieve SCIT maintenance dose (4000 BAU) during 16 weeks of treatment with dupilumab + SCIT as compared with SCIT
- Maximal tolerated SCIT dose during 16 weeks of treatment with dupilumab + SCIT as compared with SCIT
- Local skin wheal size at approximately 15 minutes after each SCIT injection during 16 weeks of treatment with dupilumab + SCIT as compared with SCIT
- Change and percent change from baseline (last pretreatment measurement) to week 17 in serum Timothy Grass sIgG subclasses other than Timothy Grass sIgG4 for dupilumab + SCIT as compared to SCIT pending on data availability

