## 5. STATISTICAL METHODS

For continuous variables, descriptive statistics will include the following: the number of patients reflected in the calculation (n), mean, standard deviation, median, first quartile (Q1), third quartile (Q3), minimum, and maximum.

For categorical or ordinal data, frequencies and percentages will be displayed for each category.

All data will be summarized by the following 4 treatment groups defined in Section 1.1.

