#### **5.7.2. Analyses of Secondary and Exploratory Efficacy Variables**

The change and percent change from baseline in continuous secondary and exploratory efficacy endpoints will be analyzed using the same approach as that used for the analysis of the primary endpoint, unless specified otherwise.

The biomarker related continuous endpoint will be analyzed using a rank based ANCOVA model with treatment and relevant baseline as covariates. Post-baseline LOCF method will be used to impute the missing data. The comparison will be performed between dupilumab +SCIT vs SCIT.

The proportion of subjects who achieve SCIT maintenance dose (4000 BAU) during 16 weeks of treatment will be compared by Chi-square test between dupilumab + SCIT and placebo for dupilumab +SCIT groups. The maximal tolerated SCIT dose during 16 weeks of treatment and the local skin wheal size at approximately 15 minutes after each SCIT injection during 16 weeks of treatment will be summarized descriptively. If the wheel size is too small to measure after the SCIT injection, the diameter is set to zero.

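### The SAP sets a comparative objective for the maximal tolerated SCIT dose but plans only by-arm description, so no between-arm estimate or interval will be reported for it

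*SAP*

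**What the plan says.** SAP 1.2.3 (Other Objectives) asks whether dupilumab improves SCIT tolerability in two ways. One is a higher proportion of subjects reaching 4000 BAU. The other is "defined as an increase in the maximal tolerated SCIT dose, comparing 16 weeks of treatment with dupilumab + SCIT" with SCIT alone. SAP 1.2.4 shows that the SAP added both to the protocol's objectives. SAP 4.5.3 lists the second as an exploratory variable, again in comparative form: "Maximal tolerated SCIT dose during 16 weeks of treatment with dupilumab + SCIT as compared with SCIT".

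SAP 5.7 makes between-arm comparison the default for efficacy variables unless something else is specified. SAP 5.7.2 specifies something else here: the maximal tolerated dose and the local wheal size after "each SCIT injection during 16 weeks of treatment will be summarized descriptively". In the same paragraph, the proportion reaching 4000 BAU "will be compared by Chi-square test between dupilumab + SCIT and placebo for dupilumab +SCIT groups".

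SAP 5 defines the descriptive statistics for continuous variables: "the number of patients reflected in the calculation (n), mean, standard deviation, median, first quartile (Q1), third quartile (Q3), minimum, and maximum". It adds that "All data will be summarized by the following 4 treatment groups defined in Section 1.1". The endpoint does not appear in the summary table of SAP 10.1, and no section says how a subject's maximal tolerated dose is derived.

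**The concern.** The objective asks whether the dose increased in one arm relative to another. The planned method describes each arm separately and stops there. A reader of the study report would see two sets of means and quartiles, with no stated difference and no measure of its uncertainty.

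The one planned between-arm comparison of tolerated dose is the chi-square test, and it reduces the dose to reached or not reached. A subject held at 3000 BAU counts the same as one held at 400 BAU. Intermediate outcomes are foreseen: Protocol 7.3.1 and SAP 2.3 both allow a reduced maintenance dose between 400 and 4000 BAU.

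The question also has some scientific weight. The Protocol Introduction lists three ways in which dupilumab may help, and the first is that it may "limit symptoms of the desensitization process so that maximal SCIT up-titration may be achieved".

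**Working it through.** **The plan's own figures.** The SAP gives no power or precision figure for this endpoint. Its only one is for the primary endpoint (25 per arm, difference 29, SD 35, two-sided 0.05, 80% power). A two-sample t-test calculation gives 81.9%, so it reproduces, but it does not bear on the tolerated dose.

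**Inputs.** From the documents: 25 per arm (SAP 2.1), the dose steps of SAP Table 2, the 4000 BAU ceiling, and the 400 BAU floor for a reduced maintenance dose (SAP 2.3). Assumed: the proportions reaching 4000 BAU, and an even spread of the remaining subjects over 400, 700, 1000, 1500, 2000 and 3000 BAU in both arms.

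**Mean difference.** The mean below target is (400 + 700 + 1000 + 1500 + 2000 + 3000)/6 = 8600/6 = 1433 BAU. With p the proportion reaching 4000, the arm mean is 4000p + 1433(1 − p). The difference is therefore (p2 − p1) × (4000 − 1433) = 2567 × (p2 − p1).

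**Precision.** The half-width is 2.01 × √[(SD1² + SD2²)/25]. For 60% against 80% the SDs are 1373 and 1098, so the half-width is 2.01 × √[(1373² + 1098²)/25] = 2.01 × 352 ≈ 707 BAU.

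**Probability of a higher dose, ties counted half.** With the same spread below target in both arms, this is p2(1 − p1) + ½p1p2 + ½(1 − p1)(1 − p2) = ½ + ½(p2 − p1).

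**Results.** Rank-sum power is from 3000 simulated trials per scenario. Chi-square power is from the normal approximation.

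| Reach 4000 (SCIT vs dupilumab + SCIT) | Mean difference, BAU | 95% half-width, BAU | Ties-half probability | Chi-square power | Rank-sum power |
|---|---|---|---|---|---|
| 60% vs 80% | 513 | 707 | 0.60 | 34%* | 33% |
| 60% vs 90% | 770 | 643 | 0.65 | 70% | 69% |
| 70% vs 90% | 513 | 607 | 0.60 | 42% | 42% |
| 50% vs 90% | 1027 | 660 | 0.70 | 90%* | 90% |

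*33.5% and 89.5% before rounding.

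Three things follow.

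- In the first and third rows the half-width exceeds the difference. For 60% against 80% the interval would run from about 513 − 707 = −194 to 513 + 707 = 1220 BAU. The planned table would show a difference of this kind but not that it is compatible with none.
- Rank-sum and chi-square power are practically equal. The ceiling makes attainment the dominant contrast, so a power gain is no argument for the change.
- Under an equal spread below target, the ties-half probability only restates the attainment difference. It adds information only if the arms also differ below 4000 BAU, and it is not in BAU. An estimate in BAU is needed beside it.

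**What the planned statistics show.** When more than half of each arm reaches 4000 BAU, both medians are 4000. The lower quartile is more informative. With 25 subjects, taking the seventh smallest value, it falls below 4000 if at least 7 subjects do. That has probability 93% when 60% reach target, 66% when 70% do, and 1% when 90% do. The arm summaries would therefore often show a real contrast.

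**The case against.** The case for leaving the plan alone is fair in several respects. The endpoint is exploratory, in a phase 2a trial without multiplicity control. SAP 5.7 permits exceptions to its comparison default, and SAP 5.7.2 makes one openly. The overlapping attainment endpoint is tested, and SCIT reactions are summarised separately by type and grade (SAP 5.8.1). Rewording the objective as descriptive would also remove the mismatch.

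A reader might infer that the trial cannot say whether the tolerated dose rose, or by how much. The documents do not support that. Means, SDs and quartiles by randomised arm give the observed direction and size, and n and SD let a reader approximate an interval. A reader might also infer that doses below 4000 BAU are ignored altogether. They enter the by-arm means and quartiles and the dosing listing of SAP 5.6.1; only the planned test ignores them.

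The most substantial objection is that the variable is undefined. Protocol 7.3.2 requires all study drugs to stop if one stops. A subject who leaves during up-titration for an unrelated reason could therefore be scored as tolerating little SCIT, and an inference on such a variable could mislead. This stands, but it argues for writing the derivation rule alongside the comparison. The by-arm means have the same defect.

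Rewording the objective would settle the wording but still leave no estimate with its precision for a question the SAP chose to add.

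**Conclusion.** The mismatch is real and minor. SAP 1.2.3 and 4.5.3 state a comparison of dupilumab + SCIT with SCIT. SAP 5.7.2 provides no between-arm estimate, interval or test for it, and the chi-square on reaching 4000 BAU does not use the gradation below that dose. The observed difference will still be visible.

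In the assumed scenarios the missing interval has a half-width of roughly 600 to 700 BAU, against differences of roughly 500 to 1000 BAU. These figures rest on assumed attainment rates and an even spread below target, because the documents give no expected distribution. The mismatch itself depends on none of these assumptions. No gain in power over the chi-square should be claimed: none appears here, and one would require the arms to differ below 4000 BAU in a way that the documents do not describe.

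**What to change.** In SAP 5.7.2, separate the maximal tolerated SCIT dose from the wheal size and add, for dupilumab + SCIT versus SCIT and labelled exploratory:

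- the difference in mean dose in BAU with a bootstrap 95% CI, saying what is reported if every subject in an arm reaches 4000 BAU, since resampling that arm then shows no variation;
- the rank-based probability that a dupilumab + SCIT subject tolerates a higher dose (ties counted half), with a 95% CI;
- the distribution by dose level in each arm.

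Rank the actual BAU dose, because a reduced maintenance dose need not fall on a step of SAP Table 2. In the same edit, define how the maximal tolerated dose is derived, including for subjects who discontinue for reasons other than SCIT intolerance. Add the endpoint to the SAP 10.1 summary.

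The cost is a short SAP edit and one exploratory table, with no new data. The downside is one more exploratory comparison without multiplicity control.
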